#### **10.4.2 Vaginal Hemorrhage**

Vaginal hemorrhage is defined in [Section 8.3.6](#) of the protocol and the assessment of vaginal hemorrhage will be collected in a specific eCRF module. Based on the eCRF module, the number of subjects with vaginal hemorrhage will be summarized for the Safety cohort.

#### **10.4.3 Pelvic Examination**

A pelvic examination will be performed at screening, Visits 4, 7P, 8, 9, and 10 to document the presence and grade (intensity) of any pain, irritation, abrasions, or lesions on the cervix or vagina using standardized criteria, and the presence and grade (intensity) of any vaginal adhesions using standardized criteria. If any lesions or abrasions are found on the cervix or vagina or vaginal adhesions are noted, another examination will be performed 2-4 days later. The grade (intensity) for each type of assessment will be summarized by visit for the safety cohort. Furthermore, a shift table will be presented summarizing the change in grade (intensity) from Visit 4 to the End-of-trial, where the End-of-trial is defined to be the last assessment in the treatment phase.

An associated listing will also be produced.

## 11 Interim Analyses

No interim analysis is planned for this trial.

## 12 Deviations from Protocol

The following changes and additions from the planned displays and analyses described in the previous version of the clinical trial protocol have been implemented in the statistical analysis plan:

- All 90% confidence intervals have been replaced with 95% confidence intervals based on FDA input on the statistical analysis plan.
- The embryo quality analysis that is described in this SAP was not mentioned in the clinical trial protocol.
- The definition of the Eligible Subjects cohort is taken to be a subject that has received at least one dose of oral contraceptives, leuprolide acetate, and MENOPUR. This aligns with the analogous cohort from the DR-PGN-302 study. In the clinical trial protocol, an “or” is used instead of an “and”.

These revisions have been implemented in the clinical trial protocol version 6.0.

## 14 APPENDICES

## Appendix 1 Notable Vital Signs

**Table 5 Notable Criteria for Vital Signs\***

Variable	Criterion Value	Change from Baseline
Systolic blood pressure	$\geq 180$ mmHg	Increase of $\geq 20$ mmHg
	$\leq 90$ mmHg	Decrease of $\geq 20$ mmHg
Diastolic blood pressure	$\geq 105$ mmHg	Increase of $\geq 15$ mmHg
	$\leq 50$ mmHg	Decrease of $\geq 15$ mmHg
Pulse rate	$\geq 120$ bpm	Increase of $\geq 15$ bpm
	$\leq 50$ bpm	Decrease of $\geq 15$ bpm
Body weight	None	Increase of $\geq 7\%$ Decrease of $\geq 7\%$
Body temperature**	$\geq 38.3^{\circ}$ C	

\* To be identified as notable abnormal, a treatment value must meet the criterion value and also the specified change from baseline.

\*\* The notable criteria is met for body temperature whenever this criteria is met.

## Appendix 2 Primary Analysis Simulation Code and the Sensitivity Analysis Operating Characteristics

### Primary Analysis Simulation Code

Below is the R code that runs the simulation described in the sample size justification.

```
#####
### LIBRARIES ###
#####

library(ggplot2)
library(tidyverse)

#####
### SETUP ###
#####

### SET THE SEED ###
set.seed(7639216)

### THE NUMBER OF SIMULATION REPS ###
n.sim <- 10000

### THE NUMBER OF SUBJECTS IN THE MODIFIED ITT ANALYSIS POPULATION ###
n.mitt <- seq(from = 100, to = 400, by = 5)

### THE TRUE PR(SPONTANEOUS ABORTION | IN THE MITT ANALYSIS POPULATION) ###
### 
p.sa <- seq(from = 0.08, to = 0.1, by = 0.01)

### A PLACE TO STORE THE RESULTS ###
sim.res <- matrix(NA, nrow = length(n.mitt), ncol = length(p.sa))
rownames(sim.res) <- n.mitt
colnames(sim.res) <- paste0(p.sa * 100, "%")

#####
### SIMULATION ###
#####

pb <- txtProgressBar(min = 1, max = length(n.mitt), style = 3)

for(a in 1:length(n.mitt)){
  setTxtProgressBar(pb, value = a)
```

```
for(b in 1:length(p.sa)){
  sim.sara <- rbinom(n = n.sim, size = n.mitt[a], prob = p.sa[b])
  sara.res <- unlist(lapply(X = sim.sara, FUN = function(x, n = n.mitt[a]){
    ifelse(binom.test(x = x, n = n, p = 0.15, alternative = c("two.sided"), conf.level =
    0.95)$conf.int[2] < 0.15, 1, 0)
  }))
  sim.res[a, b] <- mean(sara.res) * 100
}
}

#####
### PLOT THE RESULTS #####
#####

### MOLD THE RESULTS FOR PLOTTING ###
sim.res.long <- data.frame(N = as.numeric(rownames(sim.res)), SA8PCT = sim.res[, 1], SA9PCT =
sim.res[, 2], SA10PCT = sim.res[, 3]) %>%
  gather(key = "SA", value = "POWER", 2:4)

p <- ggplot(sim.res.long, aes(x = N, y = POWER, group = SA)) +
  geom_hline(yintercept = 80, linetype = "dashed", color = "grey", size = 2) +
  geom_line(aes(color = SA), size = 1.5) +
  scale_x_continuous(name = "Sample Size (in MITT Analysis Population)", breaks = seq(from =
100, to = 400, by = 20)) +
  scale_y_continuous(name = "Power", limits = c(0, 100)) +
  theme(axis.text.x = element_text(angle = 45, hjust = 1)) +
  scale_color_discrete(name = "Spontaneous\nAbortion\nRate",
  breaks = c("SA8PCT", "SA9PCT", "SA10PCT"),
  labels = c("8%", "9%", "10%"))

#####
### TABULAR OUTPUT #####
#####

### FIND WHICH RESULTS ARE ABOVE 80% POWER ###
sim.res.80 <- sim.res >= 80

### FIND THE INDICES ###
```

```
sim.res.ind <- apply(X = sim.res.80, MARGIN = 2, FUN = function(x){  
  TEMP <- length(x)  
  if(any(x)){  
    TEMP <- min(which(x))  
  }  
  TEMP  
})
```

### REPORT THE POWER FOR THESE INDICES

```
sim.table <- sim.res[sim.res.ind, ]
```

#### Hierarchical Modelling Details

Define  $n_1$  as the number of subjects in the current trial and  $Y_{1i}$  as the indicator of spontaneous abortion for the  $i^{\text{th}}$  subject in the current trial where  $Y_{1i} \sim \text{Bin}(n_1, \pi_1)$ . Let  $\pi_1$  be the true rate of spontaneous abortions in the current trial.

The previous trial (Study DR-PGN-302) reported a spontaneous rate of abortion of 55/549. This prior information about abortion rate is incorporated into the modelling framework through a hierarchical model. Dynamic borrowing between this trial's results and the current trial's data allows borrowing to occur to the extent indicated by these two data sources. More borrowing occurs when the two rates are similar while less borrowing occurs when they differ. This "dynamic" borrowing property is distinct from other approaches which use a fixed informative prior or apriori assume an amount of borrowing between these two data sources. Let  $Y_0 \sim \text{Bin}(n_0=549, \pi_0)$  where  $\pi_0$  is the true rate of spontaneous abortions from the previous trial.

We transform to the logit scale for modelling purposes. Let  $\theta_1 = \log(\pi_1/(1-\pi_1))$  and  $\theta_0 = \log(\pi_0/(1-\pi_0))$ . The hierarchical model assumes that  $\theta_0$  and  $\theta_1$  have an across studies distribution:

$$\theta_1, \theta_0 \sim N(\mu, \tau^2)$$

The across trial mean  $\mu$  and variance  $\tau^2$  are unknown and hence have a prior distribution which is combined with the data to produce estimates of  $\mu$  and  $\tau^2$ :

$$\mu \sim N(-2.2, 2.25)$$

$$\tau^2 \sim IG(0.125, 0.005)$$

The mean parameter  $\mu$  assumes a relatively vague prior on the original scale and centered at 10%. The variance component  $\tau^2$  controls the degree of borrowing among studies. Small values of  $\tau^2$  result in a greater degree of borrowing while large values of  $\tau^2$  correspond to less borrowing. The parameter  $\tau^2$  is estimated using the data, so the observed between studies variation is a key

component of the model behavior. The prior specification on  $\tau^2$  corresponds to an inverse-gamma distribution with mean 0.2 and weight 0.25.

### Operating Characteristics

The planned sample size is based only on subjects that undergo fresh embryo transfer. No further drop-outs are assumed. The analysis is evaluated across a range of true effects for the current trial's spontaneous abortion rate. For the null scenario where in truth the PVR spontaneous abortion rate is 15%, 100,000 sets of trials were simulated. For all other assumed scenarios, 5,000 sets of trials were simulated.

### Overall Success

We evaluated the overall probability that the 95% credible interval is entirely below 15% for each scenario of the true PVR rate. If PVR truly maintains an abortion rate below 15%, then this represents the power for achieving a credible interval entirely below 15%. If the true rate of abortions for PVR is 15%, then obtaining a credible interval entirely below 15% is the type I error. Results are provided in the table below.

True PVR Rate	8%	9%	10%	11%	12%	13%	14%	15%
Trial Success	0.979	0.933	0.830	0.670	0.485	0.297	0.167	0.084

When in truth the PVR spontaneous abortion rate is 9%, the trial has 93.3% power of achieving a 95% credible interval entirely below 15%. Alternatively, when in truth the spontaneous abortion rate is 15%, the trial has a 8.4% rate of success.

### Inference Associated with Various Observed Rates

For various observed rates of spontaneous abortions, the corresponding primary analysis based on the hierarchical model is described below. The posterior mean, 95% credible interval, effective number of borrowed subjects, and the borrowing percentage (out of the n=549 subjects from the previous trial) is provided. The effective number of borrowed subjects calculation  $[E(\pi_1)*(1-E(\pi_1))/Var(\pi_1)-1-240]$  is somewhat approximate as it is based on the binomial likelihood. Results are provided in the below table.

Observed Data	Estimated Rate (%) (95% CI)	Effective Number of Borrowed Subjects	Borrowing Percentage
19/240 (7.92%)	8.6% (5.7, 11.7)	103	18.9%
24/240 (10.00%)	10.0% (7.2, 13.3)	130	23.7%
36/240 (15.00%)	13.8% (10.1, 18.5)	9	1.7%

Borrowing based on the hierarchical modelling is dynamic, with higher borrowing achieved when the current trial's results are similar to the previous data and minimal borrowing when the current trial's results are at 15%. This is evidenced by both the decreasing number of borrowed subjects and the increasing width of the credible intervals. Also, based on 240 subjects being included in the

analysis, the maximal number of observed responses which maintains a 95% credible interval entirely below 15% is 28.

R2OpenBUGS Codes for Analysing the Data at the End of the Trial

```
for (i in 1:N) {  
  y[i] ~ dbin(theta[i], n[i])  
  logit(theta[i]) <- logit.theta[i]  
  logit.theta[i] ~ dnorm( mu, tau)  
}  
mu ~ dnorm(-2.2, 0.4444444)  
tau ~ dgamma(0.125, 0.005)
```

## Appendix 3 Preferred Terms Associated With Spontaneous Abortion and Ectopic pregnancy

All the preferred terms associated with Spontaneous abortion are listed below. This is based on MedDRA version 21.0. Prior to dry-run and DBL, the dictionary will be checked to make sure there is no change of terms with dictionary update.

Spontaneous abortion associated preferred terms
Abortion
Abortion complete
Abortion complete complicated
Abortion complicated
Abortion early
Abortion incomplete
Abortion incomplete complicated
Abortion induced
Abortion induced complete
Abortion induced complete complicated
Abortion induced complicated
Abortion induced incomplete
Abortion induced incomplete complicated
Abortion infected
Abortion late
Abortion missed
Abortion of ectopic pregnancy
Abortion spontaneous
Abortion spontaneous complete
Abortion spontaneous complete complicated
Abortion spontaneous complicated
Abortion spontaneous incomplete
Abortion spontaneous incomplete complicated

Abortion threatened

The relevant preferred terms associated with biochemical abortion are listed below. This is based on MedDRA version 21.0. Prior to dry-run and DBL, the dictionary will be checked to make sure there is no change of terms with dictionary update.

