a. The Screening Period may last up to 90 days from the time of signing the consent form to the start of ovarian suppression.

b. In this trial, pregnancy is defined as beginning 2 weeks prior to egg retrieval.

c. Height only measured at screening

d. Stimulation will be with MENOPUR, dosed according to the label and individualized based upon subject response at the Investigator's discretion.

e. Vaginal bleeding since the previous visit will be recorded after the start of progesterone administration until the End-of-trial visit.

f. A Pap smear done within 24 months of the Screening Visit is acceptable, provided the results are normal and a copy is obtained.

g. If Visit 4 occurs on a day where shipment to the central laboratory is not feasible, e.g. during the weekend, the subject will return to the site for blood collection on the next possible day

h. Follicle-stimulating hormone (FSH) and estradiol serum levels will be measured on Cycle Day 3 ±1 day, sampling for Anti-Müllerian hormone (AMH) serum levels must be performed prior to start of ovarian suppression.

i. Analysis by local laboratory

j. Assessment of endometrial thickness by transvaginal ultrasound at Visit 5. The ultrasounds for the embryo transfer procedure at Visit 5 and the pregnancy assessments at Visit 9 and Visit 10 can be either vaginal or abdominal. If Visit 9 is an Early Withdrawal Visit due to the subject being no longer pregnant, an ultrasound is not required.

k. Ring replacement training/confirmation training will occur.

l. PVR1, PVR2, PVR3 and PVR4 will be distributed to each subject.

m. PVR5, PVR6, PVR7 and PVR-R will be distributed to each subject.

n. PVR8, PVR9, and PVR10 will be distributed to each subject.

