### 2.1 Objectives

#### Primary Objective

- To estimate the cumulative rate of any spontaneous abortion, including spontaneous clinically recognized pregnancy loss and blighted ovum during the trial (up to Week 12 following oocyte retrieval), in subjects treated with progesterone vaginal ring (PVR) following fresh embryo transfer.

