### 3.3 Determination of Sample Size

In this safety trial, the primary assessment of interest is on the number of subjects that experience a spontaneous abortion. Because this is a single-arm trial, all subjects that enter the mITT analysis population will have been treated with the investigational product, PVR. The primary analysis involves the construction of a two-sided 95% exact confidence interval surrounding the proportion of subjects in the mITT analysis population that experience a spontaneous abortion. The upper bound of said confidence interval is then compared with the threshold of a 15% spontaneous abortion rate.

Statistical simulations have been performed to understand the operating characteristics under varying assumptions for both the sample size of the mITT analysis population and the “true” proportion of spontaneous abortions. For each simulation repetition, a sample of subjects was simulated using the binomial distribution and a given pair of sample size and “true” proportion of spontaneous abortions assumptions. A two-sided 95% exact confidence interval was then created based on the simulated data and the upper bound of this confidence interval was compared to the threshold of 0.15 (corresponding to a spontaneous abortion rate of 15%). If the upper bound of the two-sided 95% exact confidence interval was less than 0.15, the simulation repetition was declared a “success”. If, however, the upper bound of the two-sided 95% exact confidence interval was greater than or equal to 0.15, the simulation repetition was declared a “failure”. This process was repeated 10,000 times for each combination of assumed sample size and “true” proportion of spontaneous abortions. The proportion of simulation repetition successes to the total number of simulation repetitions then described the power of the proposed trial given the pair of assumptions.

The sample size necessary to achieve 80% power to exclude the possibility of a 15% spontaneous abortion rate after the use of PVR is described in [Table 2](#). If the “true” spontaneous abortion rate is 8%, 9%, or 10%, the sample size required to achieve 80% power to exclude the possibility of a 15% spontaneous abortion rate after the use of PVR is 180, 240, or 365, respectively.

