## 9 Efficacy

### 9.1 General Considerations

All confidence intervals will be two-sided 95% confidence intervals.

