### 9.2 Primary Endpoint

The primary endpoint, spontaneous abortion, is defined as two positive  $\beta$ -hCG tests occurring at least two days apart on or after 2 weeks post-oocyte retrieval, but followed by observation of any empty intrauterine gestational sac (blighted ovum), intrauterine gestation without a fetal heartbeat, or absence of viable fetuses, as documented by transvaginal ultrasound (TVUS).

The derivation of this endpoint will be as follows:

- Any subject that has two positive  $\beta$ -hCG tests at least two days apart, and
- meeting at least one of the following conditions at visit 7P (4 weeks and 3-4 days post oocyte retrieval) or at a later visit:
  1. the TVUS assessment at a later visit shows that there is no presence of gestational sac,
  2. there is a presence of empty gestational sac,
  3. there is a gestational sac that has a fetus without a heartbeat, or
  4. any AE of pregnancy loss that meets the definition of spontaneous abortion.

In order to clearly identify AEs that are spontaneous abortions, listing of all AEs related to pregnancy loss, will be generated and provided to the medical team together with the reported and coded terms. [Appendix 3](#) lists the preferred terms associated with pregnancy loss that will be used for generating this listing. This listing will be provided periodically throughout the trial. The medical team will use these listings to identify AEs that meet the spontaneous abortion definition. The identification process will be completed prior to data base lock. Since spontaneous abortion can occur outside of scheduled visits, for accurate accounting of all spontaneous abortions, the AE eCRF page needs to be included.

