#### 9.3.1 Analysis of the Primary Endpoint

The number and rate of any spontaneous abortions (occurring on or before 12 weeks following oocyte retrieval) for subjects in the mITT cohort will be summarized and the associated two-sided exact 95% confidence interval will be generated. Upon generating the two-sided exact 95% confidence interval, the upper bound of the interval will be assessed for whether it excludes or fails to exclude a spontaneous abortion rate of 15%.

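### The adverse-event search behind the primary endpoint has no term for blighted ovum or fetal death, so a loss known only from the AE page can be missed

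*SAP*

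**What the plan says.** SAP section 9.2 derives the primary endpoint for women with two positive β-hCG results separated by two days or more. From Visit 7P onward there are four routes to an event: three ultrasound findings (no sac, an empty sac, a fetus without a heartbeat) and an adverse event of pregnancy loss that fits the definition. The SAP explains the fourth route: losses can happen between visits, so the AE page has to be used.

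The AE route works through a listing sent periodically to the medical team. Appendix 3, the SAP says, "lists the preferred terms associated with pregnancy loss that will be used for generating this listing". The team works from these listings and finishes before database lock.

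Appendix 3 opens its spontaneous-abortion block with "All the preferred terms associated with Spontaneous abortion are listed below". It contains 24 terms, all beginning with Abortion. Separate blocks give one biochemical term and six ectopic terms. The only check planned for the lists is whether a dictionary update has changed a term.

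The primary objective (SAP section 2.1) covers any spontaneous abortion, "including spontaneous clinically recognized pregnancy loss and blighted ovum during the trial". The endpoint definition adds an intrauterine gestation lacking a heartbeat.

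On scans, a note to Protocol Table 6-1 states: "If Visit 9 is an Early Withdrawal Visit due to the subject being no longer pregnant, an ultrasound is not required". The ultrasounds at Visits 9 and 10 are for pregnant subjects only (Protocol sections 6.3.8 and 6.4).

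**The concern.** The fourth route exists to pick up losses that the scheduled scans do not see. The search that feeds it has no term for two of the forms of loss that the endpoint definition names. The list does not look deliberately narrow: it includes induced, threatened and ectopic abortion, so it was meant as a wide net. A check for dictionary changes would not show that a concept was absent from the start.

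The direction matters because this is a single-arm safety trial whose main comparison is with a fixed ceiling. SAP section 9.3.1 says that "the upper bound of the interval will be assessed for whether it excludes or fails to exclude a spontaneous abortion rate of 15" per cent. An event left out of the count lowers the observed rate and makes that exclusion easier.

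**Working it through.** **1. Which losses depend on the AE page.** Scheduled pregnancy scans fall at 4 weeks + 3–4 days, 6 weeks, 10 weeks and 12 weeks after retrieval. The intervals between them are about 10, 28 and 14 days. A loss seen on a trial scan at any of these visits meets one of the three ultrasound criteria and needs no AE term. A woman whose loss is diagnosed in between, for example at an outside clinic, comes to early withdrawal already known not to be pregnant, and no scan is required there. Her loss may then be in the database only as an adverse event. To go uncounted it must also be coded to a term outside Appendix 3.

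**2. The terms against the definition.**

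| Form of loss | Term naming it in Appendix 3 |
|---|---|
| Spontaneous, missed, early, late, complete or incomplete abortion | Yes, spontaneous-abortion block |
| Biochemical loss | Yes, one term |
| Ectopic pregnancy | Yes, six terms |
| Blighted ovum / empty sac | None |
| Gestation without heartbeat / fetal death | None |

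**3. The plan's own figures.** Inputs:
- Interval: "All confidence intervals will be two-sided 95% confidence intervals" (SAP 9.1), exact for the primary endpoint (SAP 9.3.1).
- Threshold 15%; 240 mITT subjects; assumed true rates of 8%, 9% and 10% (SAP 3.3).

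Upper limit for x events in n: the 97.5% quantile of Beta(x + 1, n − x). Power: P(X ≤ x_max), with X ~ Binomial(n, p) and x_max the largest x whose upper limit is below 0.15.

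| n | x_max | Power at 8 / 9 / 10%, exact | SAP Table 2 |
|---|---|---|---|
| 180 | 17 | 80.6 / 64.4 / 46.4% | 80.3 / 64.8 / 46.1% |
| 240 | 25 | 92.9 / 81.3 / 63.6% | 93.1 / 81.8 / 63.2% |
| 365 | 41 | 98.8 / 93.9 / 81.0% | 98.9 / 94.2 / 80.9% |

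The stated powers reproduce to within simulation error. The sample size is not in question.

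**4. How close the boundary is.** 25/240 = 10.42% has an upper limit of 14.99% and excludes 15%. 26/240 = 10.83% has an upper limit of 15.47% and does not.

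**5. Illustration of missed losses.** The documents give no figure for the number missed, so k is an assumption. If k losses are missed, the counted total passes whenever the true total is at most 25 + k. At a true rate of 15%:

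| k missed | P(X ≤ 25 + k), n = 240 |
|---|---|
| 0 | 2.5% |
| 1 | 3.9% |
| 2 | 5.8% |
| 3 | 8.4% |

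As a cross-check, SAP Appendix 2 says the Bayesian rule passes with up to 28 events in 240 and succeeds 8.4% of the time at a true 15%. That is the k = 3 row.

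The same point can be put as a share f of losses missed, also assumed, using P(X ≤ 25) at a counted rate of 0.15 × (1 − f). This gives 5.0% for f = 5% and 9.3% for f = 10%. At 15% the expected number of losses is 240 × 0.15 = 36, so 5% is about 1.8 losses.

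**The case against.** **Coding is unknown.** Preferred terms are outputs of coding, so the absence of a diagnosis by name does not prove a gap. If reports of blighted ovum or an absent heartbeat code to a listed term such as *Abortion missed*, nothing is lost. This stands. A reader might infer that such losses will be missed; the documents support only that they can be.

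**Sites are told what to record.** Protocol section 8.3.7 requires spontaneous abortions to be recorded as adverse events, and the protocol's definition includes blighted ovum. A site following it may well report spontaneous abortion. This lowers the risk but does not remove it, because Protocol section 8.2.2 asks for events to be recorded as diagnoses where available, and blighted ovum is a diagnosis.

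**Scans cover the named findings.** An empty sac and an absent heartbeat are themselves scan criteria, independent of coding. This stands, and confines the risk to the combination in step 1 of the working.

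**The whole count may not be biased downward.** The no-sac criterion overlaps the biochemical-abortion definition and could raise the rate. A reader might infer from this point a net bias towards excluding 15%; that is not shown. Only the direction of this one omission is clear.

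**No formal success rule.** Section 2 of both documents says that ranking the endpoints does not tie the trial's success to the primary objective. The percentages above therefore describe the 15% comparison, not a formal trial-level error rate.

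**Conclusion.** The point holds as a risk of undercounting, not as a demonstrated error. The Appendix 3 listing is the only described way for an AE-only loss to reach the primary count, and it does not name two forms of loss that the endpoint includes. Three things must coincide for a loss to be dropped: diagnosis between scheduled scans, no qualifying trial scan, and coding to an unlisted term. How often that would happen cannot be worked out from the documents.

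The size rests on assumed numbers missed. One to three uncounted losses would raise the chance of excluding 15%, when 15% is true, from 2.5% to 3.9–8.4%. These rows suppose the same number missed in every trial, and the actual number may be zero. What does not depend on that assumption is that a single event separates a result that excludes 15% from one that does not. The correction should be made because it is cheap and protects the primary count.

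**What to change.** Before database lock, reconcile by subject as well as by term. List every mITT woman with two positive β-hCG results at least two days apart who either has no ongoing pregnancy at her last scan or was withdrawn as no longer pregnant. Have the medical team classify each outcome against the endpoint definition, whatever the coded term. This does not depend on how any report codes.

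Also widen the periodic listing to all pregnancy-related adverse events, searching the reported as well as the coded terms, and amend SAP section 9.2 and Appendix 3 to say so.

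The cost is a broader listing and slightly more review time for the existing medical team. It uses data already collected and fits the deadline that section 9.2 already sets.
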